14. WBC <1,500
15. Platelets <25,000
16. Inability to take oral medication
17. Status post Transjugular Intrahepatic Portosystemic Shunt (TIPS) or scheduled to undergo procedure during trial participation

Screening visits:

At the screening visits a complete history and physical examination will be performed. Screening blood tests will be obtained to assess liver function and to verify the Child Pugh status. A pregnancy test will be done. AT phenotyping and absence of the genetic markers HLA-A*3101 and HLA-B*1502 will be confirmed. Potential subjects will be screened with the Personal Health Questionnaire-9 (PHQ-9). The PHQ-9 has been used successfully to screen adolescents over 13 years of age and adults (39). Subjects will be excluded if scoring 10 or higher on PHQ-9. An abdominal sonogram with Doppler will be performed to assess patency and directional flow of the portal and hepatic veins. Once these studies are confirmed as being consistent with the eligibility criteria arrangements will be made for the pre-treatment HVPG measurement (see below). The hepatic venous pressure gradient measurement and liver biopsy are done together as a single procedure using the transvenous route. Intravenous conscious sedation is used to carry out the procedure. Subjects will receive fresh frozen plasma if the INR >1.6 and platelet transfusion if the platelet count is <50,000 prior to the procedure to prevent bleeding as per usual clinical practice. Subjects will be carefully monitored during the procedure and in the recovery room after the procedure.

Screening Hepatic venous pressure gradient:

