2. WBC <1,000
 - a. Decrease dose by 50%
3. Neutrophil count <500
 - a. Decrease dose by 50%
4. Platelets < 20,000
 - a. Decrease dose by 50%
5. ALT > 500 IU/dl
 - a. Decrease dose by 50%
6. INR \geq 1.8 not corrected by 5 mg of vitamin K
 - a. Decrease dose by 50%

Guidelines for subsequent Study drug dose adjustments

Indications to discontinue CBZ

1. Child-Pugh score > 12
2. Hepatic encephalopathy uncontrolled with outpatient medical therapy
3. Total bilirubin > 7 mg/dL
4. Evidence of anticonvulsant hypersensitivity syndrome
 - a. Fever > 38.5 and
 - b. Lymphadenopathy, and
 - c. Erythematous, maculopapular, pruritic, or exfoliating rash
5. WBC <1,000 despite 2 weeks of Carbamazepine dose reduction, may resume therapy at 50% of starting dose when WBC > 3,000
6. Neutrophil count <500 despite 2 weeks of Carbamazepine dose reduction, may resume therapy at 50% of starting dose when ANC > 1,500
7. Platelet count <20,000 despite 2 weeks of Carbamazepine dose reduction, may resume therapy at 50% of starting dose when plt > 40,000
8. Hgb <8.5 mg/dl
9. INR \geq 2.5 not corrected by 5 mg of Vitamin K

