10. ALT > 750 IU/L
 - a. May resume previous dose when ALT < 500
11. Pregnancy
12. Liver transplantation
13. Signs or symptoms of TEN or SJS.
14. Breast feeding.
15. Allergic reaction of Grade 3 or Grade 4.
16. Evidence for behavior or ideation predisposing to suicide (increase in C-SSRS score of 1 from previous test score).

A Preliminary Study of the Efficacy and Safety of Carbamazepine in Severe Liver Disease Due to Alpha-1 Antitrypsin Deficiency

SCREENING AND MANAGEMENT FOR SPECIFIC ADVERSE EVENTS

Patients entering the study will have evidence of chronic liver disease from AT deficiency. At entry into the study, patients may have one or more of the following: elevated serum aminotransferase levels, jaundice, elevated total and direct bilirubin, medically treated ascites, esophageal and/or gastric and/or hemorrhoidal varices, biochemical evidence of hypersplenism with a white blood count (WBC) and platelet count (PLT) below the normal range, and a prolonged prothrombin time (PT) or International Normalized Ratio (INR). Adverse events will be assessed using the Common Terminology Criteria for Adverse Events (CTCAE) Version 4.0. Baseline laboratory values for patients entering the study will likely be above the normal range in the case of ALT, AST, total bilirubin, and INR and below the normal range for hemoglobin, WBC, platelets and neutrophils count. Therefore, changes in laboratory values after initiation of the study drug will need to be assessed within the context of the patient's baseline laboratory tests. We will not be reporting every variation in subject lab results as an adverse event. Small deltas from within normal limits to just outside the normal range are not clinically significant in the care of patients and should not be used to define AEs. The investigative team will use standards that define a minimum delta that determines when a change becomes an AE, either as a discrete value change or a percentage change. These can be used in combination with claims of clinical significance by the site investigator.

An increase of CP score to > 12 , development of Grade III-IV encephalopathy, or total bilirubin > 7 mg/dl will be considered a treatment failure and therapy will be discontinued. Therapy will not be restarted in these subjects even if there is an improvement in clinical status.

Alterations in liver function:

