Subjects will be excluded if they have evidence of an additional potential cause of active liver disease (e.g. infectious hepatitis, alcohol related liver disease, Wilson disease, sclerosing cholangitis, primary biliary cirrhosis). Subjects will also be excluded if they have very severe liver disease (Child-Pugh score greater than or equal to 12; serum bilirubin > 5; INR > 2.2; hepatic encephalopathy uncontrolled with outpatient medical therapy), severe renal disease (serum creatinine > 1.5 mg/dl), alcohol intake > 30 gms/day, evidence of hepatobiliary malignancy, pregnancy/lactation, portal vein or splenic vein thrombosis, severe cardiac or pulmonary disease felt to be a contraindication to CBZ therapy, HLA-B*1502-positivity, HLA-A*3101-positivity, history of suicide attempt, potential for suicide behavior based on pre-treatment screening test, severe leucopenia (wbc count < 1,500) or thrombocytopenia (platelet count < 25,000).

Total Duration of Therapy: 12 months

Forms to Complete: Informed consent signed by patient and or parent/legal guardian; entry data; visit follow up data; final report

Endpoints of the study:

1. Change in hepatic load of ATZ.
2. Change in degree of hepatic fibrosis.
3. Change in HVPG.
4. Ability to tolerate long-term course of CBZ without adverse events.

Reimbursement for study participation: Only financial assistance to cover travel related expenses.

A Preliminary Study of the Efficacy and Safety of Carbamazepine in Severe Liver Disease Due to Alpha-1 Antitrypsin Deficiency

Literature Cited

1. Perlmutter D.H., Alpha-1-Antitrypsin Deficiency, in Schiff's Disease of Liver, Schiff E.R., Maddrey W.C., Editor. 2007; Lippincott-Raven: Philadelphia. 1063-1084.
2. Perlmutter, D.H., Pathogenesis of chronic liver injury and hepatocellular carcinoma in alpha-1-antitrypsin deficiency. *Pediatr Res*, 2006; **60**: 233-8.
3. Perlmutter D.H., Autophagic disposal of the aggregation-prone protein that causes liver inflammation and carcinogenesis in alpha-1-antitrypsin deficiency. *Cell Death Differ*, 2009; **16**: 39-45.
5. Sveger T., Liver disease in alpha1-antitrypsin deficiency detected by screening of 200,000 infants. *N Engl J Med*, 1976; **294**: 1316-21.

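### The INR dose-halving trigger (1.8 or more, not corrected by vitamin K) overlaps the INR range allowed at entry (up to 2.2), so stable baseline disease can meet a toxicity rule

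*Combined protocol and SAP*

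**What the plan says.** **Entry.** INR above 2.2 is an exclusion in three places: the exclusion criteria for the screening assessment, the exclusion criteria for the treatment trial, and the Summary, where very severe liver disease includes "serum bilirubin > 5; INR > 2.2; hepatic encephalopathy uncontrolled with outpatient medical therapy". None of the three mentions vitamin K.

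**On treatment.** The section on carbamazepine or placebo dose alteration states that the dose will follow its schedule. Item 6 halves the dose when INR is at or above "1.8 not corrected by 5 mg of vitamin K". The list of indications to discontinue CBZ stops the drug at or above "2.5 not corrected by 5 mg of Vitamin K".

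**Surrounding text.** Adverse Events and Toxicity Management says that reduction or discontinuation is in general unnecessary unless one of several findings is present. One of these is progressive hepatic toxicity, with a lengthening prothrombin time among its signs. Screening and Management for Specific Adverse Events expects INR to be above normal at baseline and says that "changes in laboratory values after initiation of the study drug will need to be assessed within the context of" the patient's own baseline tests.

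**Blood counts.** Entry requires WBC of at least 1,500, and "Platelets <25,000" is an exclusion. The discontinuation list has "WBC <1,000 despite 2 weeks of Carbamazepine dose reduction, may resume therapy at 50% of starting dose when WBC > 3,000". For platelets, a subject stopped below 20,000 "may resume therapy at 50% of starting dose when plt > 40,000".

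**The concern.** A dose-reduction rule for suspected toxicity should respond to something that has happened since the drug was started. Here part of the trigger range is also part of the entry range, so a subject can qualify for the trial and for a dose cut on the same INR value.

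Three features of the dose-alteration section make this matter:

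- The schedule is worded as binding and uses absolute values.
- Reductions made for reasons other than the trough level are not mirrored in the placebo arm.
- After a reduction for a clinical or biochemical abnormality, a low trough does not allow an increase until that abnormality resolves. A stable baseline INR may never resolve.

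Two things are at stake. One is CBZ exposure in an arm of only 20 subjects. The other is the tolerability result: Objective 4 concerns safety and tolerability, and the section on the approach to safety and tolerability records laboratory abnormalities that require treatment reduction or discontinuation. A dose cut driven by unchanged cirrhosis would be recorded there alongside genuine drug effects.

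**Working it through.** The plan gives no figure of its own to reproduce on this point. The check compares limits as ranges and then illustrates the possible size.

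**1. Limits side by side**

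| Quantity | Eligible at entry | Dose halved | Drug stopped | Resume level | Dose-cut or stop range overlaps entry range? |
|---|---|---|---|---|---|
| INR | up to 2.2 | 1.8 or more, not corrected by vitamin K | 2.5 or more, not corrected by vitamin K | none stated | Yes, halving only: 1.8 to 2.2 |
| WBC | 1,500 or more | below 1,000 | below 1,000 after 2 weeks of reduction | above 3,000 | No |
| Platelets | 25,000 or more | below 20,000 | below 20,000 after 2 weeks of reduction | above 40,000 | No |
| Total bilirubin (mg/dl) | up to 5 | none stated | above 7 | not restarted | No |

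For INR, {INR ≤ 2.2} and {INR ≥ 1.8} intersect on 1.8 to 2.2, a width of 2.2 − 1.8 = 0.4. Within that band the rule is met only if vitamin K fails to correct the value. No other dose-cut or stop limit in the table falls inside its entry range.

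**2. When the rule would be met.** Child-Pugh and MELD scores are calculated at each study visit, and both use INR. A subject in the band therefore shows a qualifying value at the first on-treatment visit, subject to the vitamin K condition.

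**3. Possible size.** The documents give no baseline INR distribution. Let p be the share of subjects with an uncorrected baseline INR of 1.8 to 2.2 (an assumption). With 20 CBZ subjects (Study Design), the expected number is 20p and the chance of at least one is 1 − (1 − p)^20.

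| p (assumed) | Expected of 20 | Chance of at least one |
|---|---|---|
| 5% | 1 | 1 − 0.95^20 = 64% |
| 10% | 2 | 1 − 0.90^20 = 88% |
| 20% | 4 | 1 − 0.80^20 = 99% |

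The protocol does anticipate raised values: plasma is planned before the screening procedure when INR exceeds 1.6. That shows such values are foreseen, but not how common they are.

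**4. Resume levels.** The WBC resume level is 3,000 / 1,500 = 2.0 times the entry minimum, and the platelet level is 40,000 / 25,000 = 1.6 times. A subject enrolled with WBC of 1,500 to 3,000 or platelets of 25,000 to 40,000, and later stopped under these rules, could recover fully to baseline and still not qualify to resume. Both resume levels lie inside the eligible range, which these criteria leave open at the top.

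**The case against.** The strongest reply is that the schedule is less automatic than it looks. The toxicity section ties reduction to progressive toxicity, and a stable INR is not progressive. The dose-alteration section also has the investigators decide whether a clinical or biochemical result calls for a change. This carries some weight, but the same section says the dose will be altered by the schedule, and the numeric trigger has no exception for an unchanged value. The two statements remain unreconciled.

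Several stronger readings are tempting, and here the objection succeeds:

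- *Every subject entering with INR 1.8 to 2.2 is affected.* Not so: those whose INR vitamin K corrects are outside the rule.
- *The WBC and platelet resume levels contradict the entry limits.* They do not. They sit within the eligible range and apply only after a severe fall that persists through 2 weeks of reduced dose. Requiring more recovery before re-exposure than at first entry is coherent.
- *The baseline-context sentence already requires dose rules relative to baseline.* It leads into which laboratory changes count as adverse events. Whether it reaches dosing is not stated.
- *Halving the dose under-treats the subject and dilutes the treatment contrast.* The protocol expects that maintenance doses may be lower in liver disease and aims for a trough of 4 to 12 µg/ml. Lower exposure is a risk, but no loss of effect is shown.

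A dosing algorithm and a figure are not visible in the text available, and the heading for subsequent dose adjustments has nothing under it. Claims about how long a reduction would last should be made with that caution.

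**Conclusion.** The INR conflict stands and is wrong as written: an uncorrected INR of 1.8 to 2.2 both qualifies a subject for the trial and meets the dose-halving rule, with no change since baseline. This could lower CBZ exposure for reasons unrelated to the drug and add baseline disease to the record of abnormalities requiring dose reduction.

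The size cannot be established from the documents. The figure of 1 to 4 of 20 CBZ subjects rests wholly on the assumed share of 5% to 20%.

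A reader might infer that the on-treatment limits as a whole clash with entry. The documents do not support that: the WBC and platelet dose-cut and stop levels, the INR stop level and the bilirubin stop level all lie outside the entry ranges. The resume levels are a secondary gap to note.

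**What to change.** Reconcile three things: the INR entry limit in both exclusion lists and the Summary, the INR reduction trigger in the dose-alteration schedule, and the statement in Adverse Events and Toxicity Management that reduction is generally reserved for progressive toxicity. State explicitly whether the baseline-context sentence in Screening and Management for Specific Adverse Events governs the dose rules or only the definition of adverse events. At the same time, confirm whether it is intended that a subject who has returned to baseline WBC or platelets may still not qualify to resume.

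Which limits and which rule are right is a clinical decision for the sponsor. The cost is protocol wording in a few places, with no new data, visits or subjects.

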10. ALT > 750 IU/L
 - a. May resume previous dose when ALT < 500
11. Pregnancy
12. Liver transplantation
13. Signs or symptoms of TEN or SJS.
14. Breast feeding.
15. Allergic reaction of Grade 3 or Grade 4.
16. Evidence for behavior or ideation predisposing to suicide (increase in C-SSRS score of 1 from previous test score).

A Preliminary Study of the Efficacy and Safety of Carbamazepine in Severe Liver Disease Due to Alpha-1 Antitrypsin Deficiency

SCREENING AND MANAGEMENT FOR SPECIFIC ADVERSE EVENTS

Patients entering the study will have evidence of chronic liver disease from AT deficiency. At entry into the study, patients may have one or more of the following: elevated serum aminotransferase levels, jaundice, elevated total and direct bilirubin, medically treated ascites, esophageal and/or gastric and/or hemorrhoidal varices, biochemical evidence of hypersplenism with a white blood count (WBC) and platelet count (PLT) below the normal range, and a prolonged prothrombin time (PT) or International Normalized Ratio (INR). Adverse events will be assessed using the Common Terminology Criteria for Adverse Events (CTCAE) Version 4.0. Baseline laboratory values for patients entering the study will likely be above the normal range in the case of ALT, AST, total bilirubin, and INR and below the normal range for hemoglobin, WBC, platelets and neutrophils count. Therefore, changes in laboratory values after initiation of the study drug will need to be assessed within the context of the patient's baseline laboratory tests. We will not be reporting every variation in subject lab results as an adverse event. Small deltas from within normal limits to just outside the normal range are not clinically significant in the care of patients and should not be used to define AEs. The investigative team will use standards that define a minimum delta that determines when a change becomes an AE, either as a discrete value change or a percentage change. These can be used in combination with claims of clinical significance by the site investigator.

An increase of CP score to > 12 , development of Grade III-IV encephalopathy, or total bilirubin > 7 mg/dl will be considered a treatment failure and therapy will be discontinued. Therapy will not be restarted in these subjects even if there is an improvement in clinical status.

Alterations in liver function:

Markers of liver injury and dysfunction that will be monitored include: PT, INR, AST, ALT, GGTP, total and direct bilirubin, WBC, platelet count, hemoglobin, absolute neutrophils count, and lymphocyte count. These tests will be monitored regularly during the course of treatment, with more frequent measurements occurring in the first four months of treatment. It is anticipated that there will be fluctuations in liver biochemistries (especially ALT, AST, GGTP and alkaline phosphatase) as part of the expected clinical course of AT deficiency. It is anticipated that study subjects will have some element of hypersplenism and associated cell line reductions.

Dermatologic reactions:

Patients will be counseled regarding dermatologic signs that should be reported to a study investigator or study coordinator immediately, these include redness of the skin, blister formation, peeling, itching or oral ulceration. If these signs or symptoms occur, the study medication would be discontinued immediately and the patient would be seen within 24 hours. If the skin lesions are felt to be consistent with Stevens-Johnson syndrome (SJS) or Toxic Epidermal Necrolysis (TEN), then appropriate treatment will be initiated and the study medication will be permanently discontinued. The risk of developing SJS or TEN will be decreased as patients who carry the HLA-B*1502 and/or HLA-A*3101 gene will be excluded from the study. In addition, other less serious dermatologic changes will be assessed at each visit. The presence of mild dermatologic changes such as photosensitivity, non-specific erythema, or mild pruritus, can be observed without dose modification.

A Preliminary Study of the Efficacy and Safety of Carbamazepine in Severe Liver Disease Due to Alpha-1 Antitrypsin Deficiency

Nervous system

Mild symptoms of dizziness, drowsiness, confusion or headache have been described with CBZ. Beginning with a low dose with an incremental increase in medication on a weekly basis has been shown to reduce these side effects. It is possible these symptoms may be more pronounced when CBZ is given to patients with chronic liver disease. Patients will be monitored carefully for evidence of these symptoms.

Metabolism:

Hyponatremia can occur in patients with chronic liver disease and chronic diuretic use in the management of ascites. Therefore, its presence may reflect the natural course of liver disease. On rare occasion, inappropriate antidiuretic hormone (ADH) secretion has been associated with CBZ. Serum electrolytes will be monitored regularly as well as a “first void” urinalysis to assess specific gravity (see appended Study Flow Chart). Alterations or thyroid function studies have been reported with CBZ treatment, but they have not been associated with clinical evidence of hypothyroidism. T4 and TSH will be monitored periodically (see Study Flow Chart in Appendix 2).

Suicide

An increase in suicide in patients taking CBZ has been reported in one study (24) but numerous other studies provide strong evidence against this potential risk (25-29). Nevertheless we will monitor for suicidal tendencies very assiduously and patients will be withdrawn based on well-established guidelines (see above).

Pregnancy

Transplacental passage of CBZ to the fetus is rapid and associated with congenital malformations, including spina bifida, cardiovascular malformations, and developmental disorders.

Patients will be asked to practice effective birth control while they are taking CBZ in this study. However, given the long duration of therapy and the number of female subjects in the child-bearing age, the following precautions will be taken:

1. All female subjects of child-bearing age will undergo urine pregnancy test on enrollment, prior to starting therapy, and monthly during the trial.
2. All female subjects of child-bearing age will need to use a barrier method of contraception as CBZ has the potential to interfere with oral contraceptives
3. All female subjects of child-bearing age will be counseled monthly during the treatment portion of the trial on barrier methods of birth control.
4. If a subject is found to be pregnant, CBZ will be immediately discontinued and permanently stopped and the subject will be referred to an obstetrician for advice and consultation
5. The study will collect data on the outcomes of any pregnancies that occur in women who conceived while taking the study medication.
6. The study will collect data on the outcome of liver disease for those women whose medication was immediately discontinued.

Breast feeding

A Preliminary Study of the Efficacy and Safety of Carbamazepine in Severe Liver Disease Due to Alpha-1 Antitrypsin Deficiency

CBZ and its metabolites are transferred to breast milk and can result in transient cholestatic hepatitis[45]. The estimated dose given to a breast feeding infant is 2-5 mg/kg/day. Breast feeding will not be allowed while the mother is receiving CBZ.

Adverse events

Definition

An adverse event (AEs) is any adverse change from the patient's baseline (pre-treatment) condition, including intercurrent illness which occurs during the course of the trial, after the consent form has been signed, whether the event is considered related to treatment or not.

A serious adverse event (SAE) is an untoward medical occurrence that results in any of the following: Death, or an event that is either life-threatening (risk of death at the time of the event) requires in-patient hospitalization or prolongation of existing hospitalization, or results in persistent or significant disability/incapacity or congenital abnormality or birth defect. Important medical events that do not result in one of the events listed above may be considered a serious adverse event when, based upon appropriate medical judgment, they may jeopardize the patient and may require medical or surgical intervention to prevent one of the outcomes listed above.

A SAE which is unexpected and is drug related (even remotely) will require expedited reporting to the FDA and the University of Pittsburgh IRB in accordance with respective timeline requirements. The following events are disease outcomes and will not be considered to be serious adverse events as they can occur in the usual course of patients with AT deficiency.

1. Development of hepatocellular carcinoma
2. Complications associated with chronic liver disease which include, but not limited to
 - a. Worsening ascites
 - b. Bleeding from esophageal, gastric, or hemorrhoidal varices
 - c. Worsening hypersplenism (hard to differentiate from bone marrow toxicity)
 - d. Hepatic encephalopathy
 - e. Hepatopulmonary syndrome
 - f. Portopulmonary hypertension
3. Extra-hepatic conditions related to alpha-1 antitrypsin deficiency which include, but not limited to
 - a. Chronic obstructive pulmonary disease
 - b. Hypoxia

Data collection procedures for adverse events

Patients will be interviewed regarding medical conditions, medication changes, and symptoms that have occurred at each study visit. An AE form will be completed if any adverse event is reported.

A Preliminary Study of the Efficacy and Safety of Carbamazepine in Severe Liver Disease Due to Alpha-1 Antitrypsin Deficiency

If a study coordinator or investigator learns of any hospitalizations or other adverse events between study visits, an AE form will be completed. All AEs and SAEs from time of study entry (consent) up to the end of follow-up will be reported to the Sponsor-Investigator. A SAE form will be completed for all adverse events rated as serious. Patients will be followed for all ongoing unresolved adverse events until they are either resolved, or in the opinion of the Sponsor-Investigator or treating sub-investigator, the patient is medically stable.

The Sponsor-Investigator will assess the relationship of each adverse event to the use of study drug, based on available information, using the following as guidelines:

1. Unlikely related: No temporal association, or the cause of the event has been identified; or the drug cannot be implicated.
2. Possible related: Temporal association is present, but other etiologies are likely to be the cause; however, involvement of the drug cannot be excluded.
3. Probably related: Temporal association is present; other etiologies are possible, but unlikely.

Reporting procedures

All SAEs that are unexpected and related to study drug will be reported to the Sponsor-Investigator within 72 hours by telephone. This reporting includes serious adverse events that occur from the time the patient has signed the clinical trial consent. The Sponsor-Investigator will promptly review all SAEs and will notify the reviewing IRB and FDA within requisite time frames if an event is considered to be unexpected and possibly or definitely related to the study drug (e.g., *serious, unexpected adverse events related to the investigational drug to the agency within 15 days of the Sponsor becoming aware of such; deaths and life-threatening reactions reported to the agency within 7 days of the Sponsor's awareness*). The Sponsor-Investigator will notify all sub-investigators of unexpected SAEs related to the CBZ. Status reports on all adverse events will be generated under the direction of the Sponsor-Investigator and sent to the DSMB every month and will include the relationship of the AE to trial medication, the severity of the event and if the event is resolved or ongoing. All AEs will be reported annually to the FDA and reviewing IRB, as required

Statistical considerations

Analysis

Objective 1. Determine whether CBZ treatment reduces hepatic ATZ load in AT-deficient patients with severe liver disease.

The primary analysis will test for differences between the treated and placebo groups in the change from baseline to follow-up in the number of hepatocytes with PAS+/diastase-resistant globules using an unpaired t-test (or nonparametric equivalent if appropriate). Given the small sample size, we do not assume that randomization will balance treated and placebo groups at baseline with respect to outcome variables. Therefore, we will compare changes over the course of the treatment rather than differences at the end of the treatment. Secondary analyses will look at the area of a liver section occupied by these globules and the

A Preliminary Study of the Efficacy and Safety of Carbamazepine in Severe Liver Disease Due to Alpha-1 Antitrypsin Deficiency

steady state level of ATZ by immunoblot again using an unpaired t-test (or nonparametric equivalents if appropriate) of the differences between the treated and placebo groups in changes from baseline to follow-up.

Given that the sample is small, randomization may not balance the groups with respect to important covariates, though our ability to detect statistically significant differences is likewise limited to relatively large effect sizes. Furthermore, the number of variables that could be adjusted for in a regression model is also limited by the sample size, as is our ability to do subgroup analyses. However, as exploratory analyses, we will compare the distributions of important confounders between treated and placebo groups and fit multiple linear regression models that include independent variables, in addition to treatment group and baseline values of outcome measures, with variables whose distributions are markedly imbalanced between treatment groups.

Objective 2. Determine whether CBZ treatment reduces hepatic fibrosis in AT-deficient patients with severe liver disease.

Analysis will proceed as in objective 1; however, the outcome will be hepatic fibrosis. The primary analysis will compare treatment group differences in baseline to follow-up changes in hepatic hydroxyproline concentration using an unpaired t-test (or nonparametric equivalent if appropriate). Secondary outcome measures will include Sirius red staining of the liver. Exploratory analyses using multiple regression models will proceed as described above.

Objective 3. Determine whether CBZ treatment reduces portal pressure in AT-deficient patients with severe liver disease as assessed by serial hepatic venous pressure gradient measurements.

Analysis will proceed as in objective 1; however, the outcome will be portal pressure. The analysis will compare treatment group differences in baseline to follow-up changes in hepatic wedge pressure gradient as the outcome. An unpaired t-test (or nonparametric equivalent if appropriate) will be the primary analysis and we will conduct exploratory multiple regression analyses to adjust for the possibility of covariate imbalances as described above.

In subjects with intrahepatic collateral vessels (visualized radiologically) together with HVPG less than 10 at baseline, we will assess the outcomes in all categories other than objective 3

It is possible that we will not see a difference in hepatic ATZ load or fibrosis because of variability and heterogeneity within the liver but that the drug will produce a stabilization or improvement in overall clinical status. Therefore, as an exploratory analysis we will assess whether CBZ treatment will lead to stabilization or improvement in disease severity as measured by the MELD score. The analysis will compare treatment group differences in baseline to follow-up changes.

Analysis will proceed as above; however, the outcome will be the MELD score. Unpaired t-tests (or nonparametric equivalent if appropriate) will be the primary analysis and we will conduct exploratory multiple regression analyses to adjust for the possibility of covariate imbalances.

A Preliminary Study of the Efficacy and Safety of Carbamazepine in Severe Liver Disease Due to Alpha-1 Antitrypsin Deficiency

Power calculations

Resources limited the sample size, so we performed power calculations with an effect size estimated from prior work on the primary outcome for this study – the number of hepatocytes with PAS+/diastase-resistant globules.

The only available data come from studies we have carried out in mice. We found statistically significant differences between 18 treated and 11 placebo mice in the number of globule-containing hepatocytes after CBZ treatment. At the end of the study there were an average of 1088 (sd=260) globule-containing hepatocytes among control and 323 (sd=179) globule-containing hepatocytes among treated mice (14). Assuming that the average number of globule-containing hepatocytes at baseline was the same in the two groups of mice, then the group difference at follow-up (765 globule-containing hepatocytes) reflects the group difference in changes. Assuming equal standard deviation (sd) in the two groups, the effect size was 3.5. Then, for the proposed sample size (20 treated:10 controls) and a two-sided type I error of 5% there would be 80% power even if the effect is 1.1, about 1/3 of what was found in mice. This translates to being able to detect a drop in the treated group of 765 globule-containing hepatocytes compared to a drop in the controls of 514 (rather than 0).

For the second objective of fibrosis the only relevant data come from hepatic hydroxyproline concentrations in mice after CBZ treatment. There were statistically significant differences between the treated and placebo groups in hepatic hydroxyproline concentrations after CBZ treatment with values of 2.27 (sd=1.02) in 24 control mice and 1.21 (sd=0.70) in 25 CBZ-treated mice (14). Assuming that the hepatic hydroxyproline concentrations at baseline were the same in the two groups of mice, then the group difference at follow-up (1.06) reflects the group difference in changes. Assuming equal standard deviation (sd) in the two groups, the effect size was 1.2. Then, for the proposed sample size (20 treated:10 controls) and a two-sided type I error of 5% there would be 80% power even if the effect is 1.1, about 1/10 of what was found in mice. This translates to being able to detect a drop in the treated group of 1.06 compared to a drop in the controls of 0.106 (rather than 0).

For the third objective of portal pressure, power calculations utilized information from 3 studies in which statistically significant and clinically relevant changes in HVPG were demonstrated in small numbers of individuals treated with antiviral drugs. A drop of ~2 mm Hg, or 20%, was found in response to drug treatment (26-28). With 20 patients treated with drug and 10 treated with placebo, there would be 80% power, assuming an average drop in portal pressure of 3.4 or more mm Hg in the treated group compared with no change in the placebo group, with a standard deviation of 3 mm Hg for the measurements.

To increase recruitment, subjects in which an HPVG cannot be measured but have collateral intrahepatic vessels visualized via fluoroscopy, may be enrolled if they meet all other criteria. We expect the possibility of a loss of 20% of the patients for the primary aim due to no HVPG measurement. We expect the loss to be balanced in the intervention and placebo group. With 16 intervention/8 placebo as a sample size, we would have power to find an effect size of 1.2 demonstrating that we have adequate power.

A Preliminary Study of the Efficacy and Safety of Carbamazepine in Severe Liver Disease Due to Alpha-1 Antitrypsin Deficiency

Statistical Support, Data Management and Quality Control

The study administrator will prepare data collection forms and manuals of operations and will monitor study adherence to the trial protocol.

Safety analysis of this limited group of study subjects will be descriptive and will indicate tolerability of carbamazepine by individuals with compensated cirrhosis. Descriptive statistics of laboratory parameters at the end of therapy and at the time point of largest deviation from normal will be compiled.

The prevalence of other potential toxicities (e.g. dermatologic reactions) will also be compiled. Limited comparisons to the control group will be performed, although the study is not powered to identify relatively rare toxicities.

Approach to safety/tolerability

Clinical adverse events or laboratory value abnormalities requiring treatment reduction or discontinuation will be recorded. Particular attention will be placed upon potential serious adverse events known or believed to be related to CBZ that are fatal, potentially life threatening, significantly or permanently disabling, or require hospitalization.

Safety analysis

Adverse events. Summaries of adverse events (number adverse events, number and percentage of subjects with adverse events, rates per person-months) will be provided. Events will be summarized based on the date of onset for the event. A treatment emergent adverse event will be defined as an adverse event that begins on or after the date of first dose of study drug. Events that occur prior to the first dose of study medication or after the last dose of study medication will be summarized separately.

Summaries of the following are planned:

1. All adverse events recorded between screening and first dose of study medication.
2. All treatment emergent adverse events.
3. All emergent and related adverse events.
4. All treatment emergent hepatic adverse events.
5. All treatment emergent hematologic adverse events.
6. All adverse events that caused permanent discontinuation of study drug.
7. All adverse events that caused temporary interruption of study drug.
8. All serious adverse events and.
9. All serious and related adverse events.

Annual safety analysis will be reported to DSMB.

Laboratory abnormalities.

Laboratory results will be presented as both actual value as well as a function of normal range. Selected data (using conventional units) will be summarized by the change from baseline in laboratory test. If baseline data are missing, then any graded abnormality is considered treatment emergent.

Interim analysis.

A Preliminary Study of the Efficacy and Safety of Carbamazepine in Severe Liver Disease Due to Alpha-1 Antitrypsin Deficiency

Interim analysis of safety data will be performed after all subjects have completed 24 weeks of therapy. Interim analysis of adverse events will be made quarterly throughout the study.

Additional analyses will be performed at the request of the DSMB, if there are any concerns raised by adverse events or serious adverse events reported.

EFFORTS TO ENSURE ADHERENCE TO THE PROTOCOL

